### **Study Protocol**

#### **Background and Purpose:**

To investigate the acute effects of a single session of shoulder joint mobilization on muscle strength and proprioception in healthy individuals using a randomized, double-blind, placebo-controlled design.

#### **Study Design:**

Randomized, double-blind, placebo-controlled trial with 48 healthy university students (aged 18-25) allocated to:

- Mobilization group (n=24): passive glenohumeral joint mobilization
- Sham group (n=24): simulated mobilization without mechanical glide

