#### **Primary Outcomes:**

- Isometric shoulder muscle strength (flexion, abduction, internal/external rotation) measured by handheld dynamometer
- Proprioception assessed via laser-assisted joint position reproduction (JPR) test

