#### **Statistical Analysis Plan:**

- Normality: histograms, Q-Q plots, Shapiro-Wilk test
- Baseline group comparisons: t-tests or Mann-Whitney U
- Main analysis: linear mixed-effects models (group, time, group\*time), random effect: subject
- Software: Jamovi v2.4 with GAMLj3
- Significance: p < 0.05

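### Does the double-blind label leave the primary outcomes unprotected because it does not say who is blinded or who measures?

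*Combined protocol and SAP*

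**What the plan says.** Blinding is mentioned twice. Background and Purpose says that the question is studied "in healthy individuals using a randomized, double-blind, placebo-controlled design". Study Design repeats the label: "Randomized, double-blind, placebo-controlled trial with 48 healthy university students (aged 18-25) allocated to" two arms. The arms are given as "Mobilization group (n=24): passive glenohumeral joint mobilization" and "Sham group (n=24): simulated mobilization without mechanical glide".

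Primary Outcomes lists isometric strength in four directions, "measured by handheld dynamometer", and a second outcome: "Proprioception assessed via laser-assisted joint position reproduction (JPR) test". Data Collection Time Points gives one measurement before the session and one straight after it. The Statistical Analysis Plan section sets out "Main analysis: linear mixed-effects models" with group, time and their interaction, and a random effect for subject.

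None of these sections, nor Ethical Considerations, says who is blinded, who delivers the technique, who takes the measurements, or whether the last two are different people.

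**The concern.** In a trial of matched tablets, a double-blind label needs little explanation. In a manual-therapy trial it needs more, because the arms differ in what the operator's hands do. The person delivering the technique knows the arm, so the label must refer to the participant and someone else, and the text does not say who.

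The identity of that second party matters. Both primary outcomes are tests given by a person. They make up at least five measures: four strength directions plus joint position reproduction. The only follow-up comes straight after the session, when operator and assessor would be working close together. If the assessor knew the arm and this affected the post-session readings, the influence would enter the group-by-time term directly, and a mixed model cannot separate it from a treatment effect. Blinding an analyst instead would not protect the measurements.

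**Working it through.** **What the sections establish, side by side**

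| Party | What the text says | What can be inferred |
|---|---|---|
| Participant | Sham control; double-blind label | Probably blinded |
| Operator | Not identified | Knows the arm, because the glide is applied or withheld by hand |
| Outcome assessor | Instruments named, person not named | May be the second blinded party |
| Analyst | Not mentioned | Could also be the second blinded party |

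The label, the sham arm and an operator who knows the arm can all hold together if the assessor is a separate, blinded person. They can also hold together if the second party is the analyst. No section contradicts either reading, and none shows that blinding failed.

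**What a tester effect would do, if there were one**

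The plan states no figure on this point, so there is nothing of its own to reproduce. The inputs from the documents are 24 per arm (Study Design), two time points (Data Collection Time Points) and significance at 0.05 (Statistical Analysis Plan). Complete data and a two-sided test are assumed.

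1. With two time points and complete data, the group-by-time test is equivalent to a two-sample t-test on change scores, with df = 24 + 24 − 2 = 46.
2. Let δ be an assumed difference between arms in tester influence, in SD units of the change score, with no true treatment effect. The noncentrality parameter is δ × √(24/2) = δ × 3.464.
3. Rejection rates from the noncentral t distribution, for one outcome:

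| δ (assumed) | Noncentrality | False-positive rate |
|---|---|---|
| 0 | 0 | 0.050 |
| 0.1 | 0.346 | 0.063 |
| 0.192 | 0.665 | 0.100 |
| 0.3 | 1.039 | 0.174 |

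4. The value 0.192 was found by solving for a doubled error rate, so the 10% beside it reflects that target and is not evidence about this trial.
5. In SD units of the raw outcome, δ = 0.192 corresponds to 0.192 × √(2(1 − r)), where r is the baseline-to-post correlation. This gives 0.19 at r = 0.5, 0.12 at r = 0.8 and 0.09 at r = 0.9. The documents do not give r either.

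The table shows that a modest tester influence would matter if it existed. It does not show that one exists, because no SD, reliability or tester effect appears anywhere in the documents.

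**What naming the parties would change**

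The outcomes, time points, model, threshold and sample size would all stay as they are. If the assessor is blinded, the added sentence would record what the label already suggests. If not, it would correct the description and state a limitation. In neither case is there an analytic rule in the plan to repair.

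**The case for a change.** The strongest case for acting is that the plan claims double-blinding twice, and its main result depends on that claim for tests given by a person. A reader should be able to check it. The sponsor knows the answer, stating it costs one sentence, and the possible readings do not protect the measurements equally. Brevity explains the silence but does not fill it.

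Much of this stands. The text does leave the parties unnamed, and a blinded assessor is an inference. It would go too far to say that the label guarantees one, or that assessor blinding alone would make the group-by-time result sound. With at least five primary measures, the 5% rate above applies only to one of them.

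What does not follow is a defect in the plan. The document is an outline in short bullets, and it does not describe the operator or the randomization method either. Its silence about the assessor is part of that general economy and does not point to an unblinded measurement. Ethical Considerations reports that consent was obtained from all participants, so enrolment may already be complete. In that case a new sentence could only record what was done, and the trial report is the natural place for that.

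**Conclusion.** The observation is accurate as a matter of reporting: the blinded parties and the outcome assessor are not named in any section from Background and Purpose to Ethical Considerations. It does not call for a change to the plan. There is no contradiction and no rule that would produce a wrong result. Any wording that named the parties would leave the design and analysis untouched.

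No error rate can be attached to the gap from the documents. If the assessor is unaware of the arm, this source adds nothing to the nominal 5% on a given outcome. The figures of about 6%, 10% and 17% apply only if the assessor knew the arm and this shifted the change scores by an assumed 0.1, 0.19 or 0.3 SD.

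This conclusion rests on treating the label as a good-faith description. Evidence that the operator took the measurements would raise a different and more serious question, but the documents contain none. Readers of the eventual report will reasonably expect it to say who was blinded and who measured.

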#### **Primary Outcomes:**

- Isometric shoulder muscle strength (flexion, abduction, internal/external rotation) measured by handheld dynamometer
- Proprioception assessed via laser-assisted joint position reproduction (JPR) test

#### **Data Collection Time Points:**

- Baseline
- Immediately after intervention

#### **Statistical Analysis Plan:**

- Normality: histograms, Q-Q plots, Shapiro-Wilk test
- Baseline group comparisons: t-tests or Mann-Whitney U
- Main analysis: linear mixed-effects models (group, time, group\*time), random effect: subject
- Software: Jamovi v2.4 with GAMLj3
- Significance: p < 0.05

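### The planned mixed model is in effect a change-score comparison: valid, but adjusting for the baseline already collected is more precise unless the baseline slope is near 1

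*Combined protocol and SAP*

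**What the plan says.** The Study Design section allocates 48 participants equally, 24 to each arm ("Mobilization group (n=24): passive glenohumeral joint mobilization", and the same number to sham). Data Collection Time Points lists baseline and one further occasion, "Immediately after intervention". Primary Outcomes lists "Isometric shoulder muscle strength (flexion, abduction, internal/external rotation) measured by handheld dynamometer" and "Proprioception assessed via laser-assisted joint position reproduction (JPR) test", which makes at least five measures.

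For all of them the Statistical Analysis Plan section gives one model form: "Main analysis: linear mixed-effects models (group, time" and the group-by-time interaction as fixed effects, with "random effect: subject". No baseline covariate is listed. Baseline values otherwise appear only in "Baseline group comparisons: t-tests or Mann-Whitney U", which does not enter the treatment estimate. The section does not say which model term is the treatment effect, how many trials are taken per occasion, or how missing data are handled.

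**The concern.** With only two occasions, a random-intercept model with a group-by-time interaction has little to add to a comparison of change scores. A change score subtracts the whole baseline value, so it assumes that a participant one unit higher at baseline is expected to be one unit higher afterwards. Measurement error and regression to the mean usually pull that slope below 1. The change score then carries baseline noise that an adjusted analysis would remove.

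Precision is at stake, not validity. With 24 per arm, intervals for every primary measure could be wider than the collected data require. Conditionally on a chance baseline imbalance, the planned estimate is shifted by -(1 - slope) times that imbalance. The shift averages to zero over randomisations and is the same loss seen from another side, not an additional one.

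**Working it through.** **Inputs.** From the documents: 24 per arm, two occasions, and the model terms. Assumed: r (baseline-post correlation), k (post SD / baseline SD), two-sided 5% tests. The documents give no power, effect size, SD or correlation, so the sample size of 48 cannot be reproduced.

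**Step 1: is the planned test a change-score test?** The random-intercept model was fitted by REML to simulated data of this size, with one value per subject per time. In two data sets the interaction and the difference in mean change agreed in both estimate and SE: 0.1858 (SE 0.2651) and 0.1664 (SE 0.2769). In three more, at r = 0.3, 0.6 and 0.9, the t values agreed: 2.126, 1.902 and 3.809. The match needs a positive subject-variance estimate. The within-group covariance was negative in about 2% of simulated trials at r = 0.3 and almost never at r = 0.5 or above.

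**Step 2: variance ratio.** Take the baseline SD as 1 and write b = rk for the slope.

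- Change score, per-subject variance: 1 + k² - 2rk = (1 - b)² + k²(1 - r²).
- ANCOVA, per-subject variance: k²(1 - r²), times 1 + 1/44 = 45/44 for estimating the slope, because E[1/chi-square(46)] = 1/44 under normality.
- Ratio, ANCOVA/planned: k²(1 - r²)(45/44) / (1 + k² - 2rk).

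Example, k = 1, r = 0.5: 0.75 × 1.0227 / 1 = 0.767.

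| k | r = 0.3 | r = 0.5 | r = 0.7 | r = 0.9 |
|---|---|---|---|---|
| 0.8 | 0.51 | 0.58 | 0.64 | 0.62 |
| 1 | 0.66 | 0.77 | 0.87 | 0.97 |
| 1.25 | 0.80 | 0.91 | 1.00 | 0.97 |

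Interval width scales with the square root. For k = 1: √0.665 = 0.82, √0.767 = 0.88, √0.869 = 0.93, √0.972 = 0.99.

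**Step 3: where the gain ends.** The ratio can be written (45/44)/(1 + d²), with d = (1 - b)/(k√(1 - r²)). It is below 1 when |d| > 1/√44 = 0.151, that is, when the slope differs from 1 by more than 0.151 × (residual SD / baseline SD). At b = 1 the ratio is 45/44 = 1.023, the worst case. At k = 1 the break-even is r = 88/45 - 1 = 0.956. At k = 0.8 the ratio never exceeds 0.65. There is no gain for r from 0.82 to 0.95 at k = 1.1, or from 0.69 to 0.87 at k = 1.25.

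**Step 4: power and sample size.** Take a hypothetical effect with 80% power under the planned model. ANCOVA power is Φ(2.80/√ratio - 1.96).

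| k | r = 0.3 | r = 0.5 | r = 0.7 | r = 0.9 |
|---|---|---|---|---|
| 0.8 | 97% | 96% | 94% | 94% |
| 1 | 93% | 89% | 85% | 81% |
| 1.25 | 88% | 83% | 80% | 81% |

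The low point is 79%, at k = 1.25, r = 0.8. The planned model would need 24/ratio per arm to match ANCOVA with 24 per arm: about 36, 31, 28 and 25 at k = 1, and 30, 26, 24 and 25 at k = 1.25.

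**Step 5: simulation.** With normal data, 40,000 replicates and k = 1, the ratios were 0.663, 0.765, 0.870 and 0.970 at the same r values. Type I error was 0.049 to 0.051 for both analyses. With log-normal data (skewness about 2.3, equal SDs) the ratios were 0.62, 0.73, 0.81, 0.89 and 0.93 at r = 0.26, 0.46, 0.66, 0.88 and 0.96. Type I error was then 0.045 to 0.048 for both.

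**The case against.** The strongest reply is that nothing here is broken. A prespecified interaction test in a randomised two-occasion trial is unbiased and holds its error rate. The size of any gain rests on r and k, which the documents do not give. Strength measured twice around a single intervention may correlate highly, and at k = 1, r = 0.9 power rises only from 80% to 81%. Any larger gain may be confined to joint position reproduction, whose scoring is not described. Variance ratios also look more impressive than the narrowing of intervals they produce.

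All of that stands as a limit on the size of the benefit. It does not reverse the recommendation, because the loss is bounded at 2.3% of variance while the possible gain is tens of percent of variance. The choice therefore does not depend on knowing r.

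Two further points also stand. The exact equivalence fails if repeated trials enter as separate rows or data are missing, and the ratios then describe only one possible implementation. A late change of main analysis also has a credibility cost. The Ethical Considerations section reports consent in the past tense for all participants, which may mean that enrolment is complete.

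**Conclusion.** The point holds as an efficiency improvement. The equivalence and the formulas are firm under the stated conditions: complete data, one value per subject per time, a positive subject-variance estimate, and the interaction read as the treatment effect. The benefit in this trial is uncertain because r and k are assumptions. Over the values tabulated, it runs from a 49% reduction in variance (k = 0.8, r = 0.3) to essentially none (k = 1.25, r = 0.7), and the worst case is a loss of about 2% when the slope is 1. The change is worth making because it uses measurements already planned and its statistical cost is small and bounded. The planned analysis would not give an invalid answer if left as it is.

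**What to change.** In the Statistical Analysis Plan section, replace the main-analysis item with wording such as:

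> For each primary outcome, the post-intervention value (the mean, if several trials are taken) is regressed on group and the baseline value of the same outcome (ANCOVA). The group coefficient with its 95% confidence interval is the treatment effect. The mixed model with group, time and their interaction is a sensitivity analysis.

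This also names the treatment-effect term, which the plan leaves open. It needs no new data and costs one degree of freedom. Because the main analysis changes, it requires a dated amendment before unblinding; keeping the mixed model as a sensitivity analysis limits the credibility cost. If unblinding has already taken place, the prespecified mixed model should remain the main analysis and ANCOVA should be reported as supportive.

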#### **Ethical Considerations:**

- Approved by Acibadem University and Acibadem Healthcare Institutions Medical Research

Ethics Committee (ATADEK) with the approval number 2025-04/185

- Informed consent obtained from all participants
- Registered at ClinicalTrials.gov (NCT06910332)

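### Several primary outcomes share one unadjusted 0.05 threshold: with five tests and no true effect, at least one is significant in 22.6% of trials if independent, about 10–18% at assumed correlations of 0.9–0.5

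*Combined protocol and SAP*

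**What the plan says.** The Primary Outcomes section has two bullets. The first is "Isometric shoulder muscle strength (flexion, abduction, internal/external rotation) measured by handheld dynamometer" and the second is "Proprioception assessed via laser-assisted joint position reproduction (JPR) test". Neither is placed above the other, and no composite strength score is defined.

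The Statistical Analysis Plan specifies the model as "Main analysis: linear mixed-effects models (group, time, group\*time), random effect: subject" and the decision criterion as "Significance: p < 0.05". It does not say how many models will be fitted, how results from several primary outcomes will be combined, or what would count as a positive trial. No other section supplies such a rule. The Study Design section describes a "Randomized, double-blind, placebo-controlled trial with 48 healthy university students", split 24 and 24.

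**The concern.** When several outcomes are all called primary and each is judged at 0.05, the chance that at least one is significant by luck exceeds 0.05. The plan has no rule preventing one isolated significant strength direction, or JPR alone, from being presented as the trial's positive primary result. A reader of the eventual report could not separate such a finding from the background rate of chance findings.

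How serious this is depends on how many tests there are and how strongly they are correlated. The plan fixes neither, so both are varied below.

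**Working it through.** **The plan's own figure.** There is none to reproduce: the documents give no familywise error rate, power, effect size or standard deviation.

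**Inputs**
- Per-test level 0.05 (Statistical Analysis Plan). Sidedness is not stated; two-sided is assumed.
- Number of tests, k (Primary Outcomes). Flexion, abduction, internal rotation, external rotation and one JPR score give k = 5. If internal/external rotation is a single ratio, k = 4. If each bullet is one outcome, k = 2. Four JPR scores, as an illustration, would give k = 8.
- 24 per arm (Study Design) and two time points (Data Collection Time Points), so each outcome has one group-by-time contrast.
- Correlation ρ between test statistics: not in the documents, assumed from 0 to 0.9.

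**Independent tests.** P(at least one significant) = 1 − 0.95^k.
- k = 2: 1 − 0.9025 = 9.75%
- k = 4: 1 − 0.8145 = 18.5%
- k = 5: 1 − 0.7738 = 22.6%
- k = 8: 1 − 0.6634 = 33.7%

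**Equally correlated tests.** With c = 1.96 and φ, Φ the standard normal density and distribution function,

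P = 1 − ∫ φ(u) [Φ((c − √ρ·u)/√(1−ρ)) − Φ((−c − √ρ·u)/√(1−ρ))]^k du.

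For k = 5:

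| ρ | Either direction | Improvement only |
|---|---|---|
| 0 | 22.6% | 11.9% |
| 0.3 | 20.9% | 10.5% |
| 0.5 | 18.3% | 9.1% |
| 0.7 | 14.8% | 7.4% |
| 0.9 | 10.2% | 5.1% |

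The improvement-only column drops the lower tail; at ρ = 0 it is 1 − 0.975^5 = 11.9%. Its benchmark is 2.5% for a single two-sided test.

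For k = 4 the either-direction rate is 15.6% at 0.5 and 9.4% at 0.9. For k = 8 it is 25.0% at 0.5.

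**JPR independent of strength.** If only the four strength measures are correlated, P = 1 − (1 − P₄) × 0.95, where P₄ is the rate for the four strength tests. This gives 19.8%, 17.4% and 13.9% at strength correlations of 0.5, 0.7 and 0.9.

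**Check at the trial's size.** With two time points, complete data and a random intercept, the group-by-time test is a two-sample t-test on change scores with 46 degrees of freedom. Simulating five such tests with 24 per arm gave 22.4%, 18.4% and 10.3% at ρ = 0, 0.5 and 0.9, in line with the table.

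**Under Holm, k = 5.** The ordered p-values are compared with 0.05/5 = 0.01, then 0.05/4, 0.05/3, 0.05/2 and 0.05, stopping at the first failure. Simulated familywise error was 4.9%, 4.6%, 4.3%, 3.6% and 2.4% at ρ = 0, 0.3, 0.5, 0.7 and 0.9.

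For power, take an outcome with an assumed 80% unadjusted power, which at 24 per arm means a difference of about 0.83 SD of the change score. Under Holm its power is 69% at ρ = 0, falling to 65% at ρ = 0.9, if all five effects are real. It is about 57% if only that one is.

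**The case against.** The strongest reply is that the harm requires an any-one-wins claim that the documents never make. The stated purpose concerns strength and proprioception, which can be read as two separate questions. If each outcome is reported and interpreted on its own, each statement keeps its 5% error. In a small single-session study of healthy volunteers, whether such questions need joint control is partly a matter of preference. If success required every outcome to be significant, there would be no inflation at all.

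Three further points are fair.
- Separate testing of each direction is inferred from the single threshold and the absence of any other rule; the plan does not say it outright.
- The count of five is the natural reading, not the only one, and two domain-level outcomes would give less than half the 22.6%.
- The 10–18% range assumes JPR correlates with strength as closely as the strength directions correlate with each other. Treating JPR as independent gives 14–20%, which is arguably more plausible.

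These points limit how precisely the size can be stated, but they do not remove the problem. Every reading with more than one separately tested primary outcome, and no rule requiring all to succeed, exceeds 5%. Per-outcome interpretation and an all-must-succeed rule are both possible intentions, but neither is written down. Labelling every outcome primary leaves the any-one-wins reading open.

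**Conclusion.** The concern holds. This is an omission, not a contradiction, because the plan claims no familywise rate. Followed as written, it lets a single significant group-by-time effect count as a positive primary result. On the five-outcome reading that happens by chance in roughly 10% to 23% of trials with no true effect, about 2 to 4.5 times the nominal 5%. The chance of a false improvement on at least one outcome is about half that.

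The result rests on two-sided testing, separate tests for each outcome, a count of five, and assumed correlations from 0 to 0.9. The absence of a rule is certain; the exact size is not. It should be fixed, but it does not invalidate the trial.

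**What to change.** Keep the 0.05 criterion as the general standard and add wording to the Statistical Analysis Plan along these lines:

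> The primary family consists of the group-by-time effect for each primary outcome: the four strength directions and one JPR score, defined before unblinding. Familywise error across this family is held at two-sided 0.05 by the Holm procedure. A primary outcome is called positive only if its Holm-adjusted p-value is below 0.05.

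Two definitions must be settled first: which JPR score is used, and whether internal/external rotation is one ratio (the family is then four) or two measures. An acceptable alternative is to name one primary outcome and list the others as secondary.

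The text says "Informed consent obtained from all participants", so the study may already be under way. The change should be dated and made before results are unblinded; if that is no longer possible, it should be reported as a post hoc adjustment.

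The cost is a short addition to the plan and no new data. Because the sample is fixed at 24 per arm, Holm carries the power loss shown above. Naming a single primary outcome avoids that loss but gives up confirmatory claims on the other four.
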